Patients will be assessed weekly for 4 weeks during buprenorphine versus placebo treatment. The dosage of buprenorphine will be adjusted according to a prespecified protocol. Blood samples will be collected to assess for opioid activity (e.g., serum prolactin levels), drug blood levels, pupillary response, and their relationship to anti-suicidal effects. After 4 weeks buprenorphine or placebo will be discontinued and patients followed for 2 weeks to assess buprenorphine discontinuation symptoms, and recurrence of suicidal ideation.

[figure not shown]
Study Duration:

The entire project is estimated to take approximately 42 months broken down into 36 months of data collection and 6 months of analysis.

Participant Duration:

The total duration for each participant from the time of screening to study completion is approximately 10 weeks.

1.4. Schema:

1.5. Schedule of Activities:

	Screen	Study Visits									
						Week 1	Week 2	Week 3	Week 4	Week 5	Week 6/ EOS
		Baseline	Day 1	Day 3	Day 5	Day 10	Day 17	Day 24	Day 31	Day 38	Day 45
					Phone	+/- 2 d	+/- 2 d	+/- 2 d	+/- 2 d	+/- 2 d	+/- 2 d
Inclusion/Exclusion Criteria	X										
Demographic data	X										
Consent	X										
Medical and Psychiatric History	X										
Physical Exam		X									
Neurological Exam		X	X**** *								X
Vital Signs		X	X	X		X	X	X	X	X	X
ECG*											X
Chemistry & CBC*		X									
Urine Toxicology Screen		X	X								
Urine Pregnancy Test		X	X								
Mini-International Neuropsychiatric Interview (M.I.N.I.)	X										
Massachusetts General Hospital Antidepressant Treatment Response Questionnaire (MGH-ATRQ)	X										
Montgomery-Åsberg Depression Rating Scale (MADRS)	X	X	X	X	X	X	X	X	X	X	X
Columbia Suicide Severity Rating Scale (C-SSRS)	X	X	X	X	X	X	X	X	X	X	X
Scale for Suicidal ideation (SSI)	X	X	X	X		X	X	X	X	X	X
Hamilton Depression Rating Scale 21-item (HAMD-21)	X	X	X	X	X	X	X	X	X	X	X
Hamilton Depression Rating Scale 6-item (HAMD-6)			X								
Clinical Global Impressions Severity (CGI-S)	X	X	X	X	X	X	X	X	X	X	X

	Screen	Study Visits									
						Week 1	Week 2	Week 3	Week 4	Week 5	Week 6/ EOS
		Baseline	Day 1	Day 3	Day 5	Day 10	Day 17	Day 24	Day 31	Day 38	Day 45
Adverse Childhood Experience (ACE) Questionnaire		X									
Snaith–Hamilton Pleasure Scale (SHAPS)				X		X	X	X	X	X	X
Beck Hopelessness Scale		X	X	X		X	X	X	X	X	X
Beck Depression Inventory II (BDI-II)		X	X	X		X	X	X	X	X	X
Ruminative Responses Scale				X		X	X	X	X	X	X
Insomnia Severity Index (ISI)		X		X		X	X	X	X	X	X

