Brief Pain inventory (BPI)		X		X		X	X	X	X	X	X
Ketamine Infusion			X								
Pupillometry****			X	X		X	X	X	X	X	
Implicit Association Test-IAT		X		X					X		
Randomization (buprenorphine/placebo)				X							
Buprenorphine 0.2mg-0.8mg (10 SL/wk) Dispensed***				X		X	X	X			
Ketamine & Metabolites Blood Levels**			X								
Buprenorphine & Metabolites Blood Levels							X		X		
Prolactin Blood Levels			X **			X	X	X	X	X	
Clinician-Administered Dissociative States Scale (CADSS)**			X								
Visual Analogue Scale (VAS)**			X								
Subjective Opiate Withdrawal Scale (SOWS)										X	X
Clinician Opiate Withdrawal Scale (COWS)										X	X
Concise Health Risk Tracking Scale Self-Report (CHRT-SR)		X					X		X	X	X
Adverse Event Review		X	X	X	X	X	X	X	X	X	X
Concomitant Medication Review	X	X	X	X	X	X	X	X	X	X	X

*if no results within the past 6 months

**-.5 min, 40, 80, 120, 180, 220 min

*** Weekly supply of rx provided. Varying dosage depending on response & tolerability.

****-.5min, 40 min

***** @220 min / discharge

2. Introduction:

2.1. Background:

Opiate abuse and addiction have become major public health problems in the United States over the past decade (1). The profound increase in accidental deaths due to opioid overdose is accompanied

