Opioid activity of ketamine as well as buprenorphine	Peripherally by exploring opioid activity in subjects treated in the ketamine infusion and the sublingual buprenorphine vs. placebo phases by measuring serum metabolites of both ketamine and buprenorphine. The metabolites are measured in ng/mL with	Day 1 and 3-31.

	a reference interval of 1-10. Any presence of the drug will result in a number within the interval. If none detected, a not established level will be the result.	
Serum prolactin level	Levels of the hormone prolactin may be increased by opioids and ketamine in serum.	Change from Day 3-31.
Pupillometry	Moreover, we will apply pupillometry to estimate opioid activity. Levels of drug and opioid activity at specific time points will be correlated with response at that time point. In addition, regression analyses will be used to assess the relative contribution of opioid activity in blood, drug blood level, and pupil measure to improvement in suicidal behavior as well as mood, pain, and insomnia. This aim is exploratory.	

4. Study Design:

5. Study Population:

5.1. Inclusion criteria:

A subject will be eligible for inclusion only if all of the following criteria are met:

1. Male or female, 18 to 70 years of age, inclusive, at screen.
2. Able to read, understand, and provide written, dated informed consent prior to screening. Participants will be deemed likely to comply with study protocol and communicate with study personnel about adverse events and other clinically important information.
3. Diagnosed with Major Depressive Disorder (MDD), single or recurrent or Bipolar-II Disorder and currently experiencing a Major Depressive Episode (MDE) of at least eight weeks in duration, prior to screening, according to the criteria defined in the Diagnosis and Statistical Manual of Mental Disorders, Fifth Edition (DSM-5). The diagnosis of MDD will be made by a site psychiatrist and supported by the Structured Clinical Interview for DSM-5 (SCID-I/P).
4. Has a history of TRD during the current MDE, as assessed by the investigator. TRD is defined as failure to achieve a satisfactory response (e.g., less than 50% improvement of depression symptoms), as perceived by the participant, to at least one "treatment course" of a therapeutic dose of an antidepressant therapy of at least 8 weeks duration. The adequacy of dose and duration of the antidepressant therapy will be determined as per the MGH ATRQ criteria.

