24. Current (or chronic) use of opiates.
25. Current use of Lamictal and an inability to stop the medication prior to receiving ketamine.

5.3. Screen Failure:

Screen failures are defined as participants who consent to participate in the screening portion of the study (i.e., sign our screening ICF) but are not subsequently randomly assigned to the study intervention or entered in the study. A minimal set of screen failure information is required to ensure transparent reporting of screen failure participants, to meet the Consolidated Standards of Reporting Trials (CONSORT) publishing requirements and to respond to queries from regulatory authorities. Minimal information includes demography, screen failure details, eligibility criteria, and any serious adverse event (SAE).

Individuals who do not meet the criteria for participation in this trial (screen failure) due to a specific modifiable factor may be rescreened at a later date once appropriate study criteria are met. Rescreened participants will be assigned the same participant number as for the initial screening.

In the case of screen failure, screening data of such patients will be electronically stored in our REDCap database.

6. Study Intervention:

Patients will receive an infusion of ketamine at 0.5mg per kg over 40 minutes. Ambient light will be lowered and patients are accompanied during and after the completion of the infusion until discharge. Patients will be assessed clinically at 3 hours and then at day 3. After the ratings are completed on Day 3, patients will be started on sublingual medication—buprenorphine or matched placebo beginning at 0.2 mg per day. Patients will be assessed weekly for 4 weeks. Doses will be adjusted at each session to a maximum of 0.8 mg after 3 weeks. Increases will be by 0.2mg increments. Participants will receive their study medication during weekly visits and will be instructed to self-administer it at home, ensuring the drug fully dissolves within 20 minutes before ingestion. As with our previous ketamine study, patients will be asked to maintain their other medications throughout the study as feasible. At the end of the active treatment phase, patients will discontinue the study drugs and will be followed up on Days 38 and 45 to monitor for any signs of withdrawal.

7. Participant discontinuation/withdrawal

7.1. Discontinuation of Study Intervention:

Subjects may be withdrawn from the study by the Principal Investigator if a subject:

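### Buprenorphine levels at Days 17 and 31 are not tied to the time of the home dose, which adds avoidable error to the exploratory level–response analysis

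*Combined protocol and SAP*

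**What the plan says.** The table in section 3 (Objectives and Endpoints, rows under Other) uses the drug level as a number, not only as evidence that the drug was taken. It plans a same-visit correlation, "Levels of drug and opioid activity at specific time points will be correlated with response at that time point", and adds that "regression analyses will be used to assess the relative contribution of opioid activity in blood, drug blood level, and pupil measure to improvement in suicidal" behaviour and to mood, pain and insomnia. It closes with "This aim is exploratory".

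In section 1.5 (Schedule of Activities) the row "Buprenorphine & Metabolites Blood Levels" is marked at two visits, which by column position are Day 17 and Day 31. Both carry a window of plus or minus 2 days. The row has no footnote and no sampling time. In the same table the row "Ketamine & Metabolites Blood Levels" carries a footnote with six times in minutes, from just before the infusion to 220 minutes.

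On dosing, section 6 says: "Participants will receive their study medication during weekly visits and will be instructed to self-administer it at home". Section 9 describes treatment as daily, with the dose raised weekly. The daily dose ranges from 0.2 to 0.8 mg. On the end of treatment, section 1.3 says: "After 4 weeks buprenorphine or placebo will be discontinued and patients followed for 2 weeks". The documents do not give an hour of dosing, say whether a dose is taken before the draw on a visit day, ask for the time of the last dose, or adjust the analysis for it.

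**The concern.** For any drug with a finite half-life, two patients with the same overall exposure will show different levels if one is sampled 2 hours after a dose and the other 20 hours after. An untimed level is thus an error-prone measure of exposure. If dose timing is unrelated to response, the error pulls the level–response correlation towards zero. If timing is related to response, for instance through adherence, the bias can go either way. In the planned regressions, a drug level blurred in this way may also appear to contribute less than it does.

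At most 30 patients, the active arm, can supply a buprenorphine level, so there is little precision to spare. A null result could not be told apart from timing noise, and dose times that are not asked for at the draw cannot be recovered reliably later.

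**Working it through.** The documents state no power, precision or expected size for the level–response correlation, so there is no figure of the plan's own to reproduce. The sample-size statement in section 9 concerns the SSI comparison and does not enter here. What follows is illustration on stated assumptions.

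**Inputs from the documents.** Daily dosing (section 9); 30 patients per arm (section 1.3, Study Population); doses of 0.2 to 0.8 mg (section 1.3, Description of Study Intervention); draws at Days 17 and 31 (section 1.5).

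**Assumptions.** Half-life 6, 12, 24 or 36 h; absorption rate 1 per hour; one compartment, 14 daily doses superimposed; between-patient coefficient of variation (CV) of exposure 30% or 50%; time since dose uniform over 1–24 h (nearly the widest spread that daily dosing allows) or over 2–14 h.

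**Formulas.** Let V be the variance of the log level produced by timing alone, and B = ln(1 + CV²) the between-patient log variance. B is ln(1.09) = 0.0862 at 30% and ln(1.25) = 0.2231 at 50%. The observed correlation is the true one multiplied by √[B/(B + V)].

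| Half-life | Peak/trough | V, 1–24 h | Multiplier (CV 30% / 50%) | V, 2–14 h | Multiplier (CV 30% / 50%) |
|---|---|---|---|---|---|
| 6 h | 10.77 | 0.5416 | 0.37 / 0.54 | 0.1435 | 0.61 / 0.78 |
| 12 h | 3.22 | 0.1316 | 0.63 / 0.79 | 0.0346 | 0.84 / 0.93 |
| 24 h | 1.78 | 0.0322 | 0.85 / 0.93 | 0.0084 | 0.95 / 0.98 |
| 36 h | 1.47 | 0.0142 | 0.93 / 0.97 | 0.0037 | 0.98 / 0.99 |

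Example: 12 h, 1–24 h, CV 30% gives √[0.0862/(0.0862 + 0.1316)] = √0.396 = 0.63.

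**Cross-check with a simpler model.** With log-linear decline, V = (ln 2/half-life)² × (range)²/12. For 24 h and a 0–24 h spread, V = (0.0289)² × 48 = 0.040. At CV 50% the timing share is 0.040/(0.040 + 0.2231) = 15%, and the multiplier is √0.85 = 0.92. This agrees with the 0.93 above.

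**Effect of differing doses.** If patients were spread evenly over 0.2, 0.4, 0.6 and 0.8 mg (an assumption), the dose itself would have a CV of 0.224/0.5 = 45% and a log variance of 0.271. Adding this to B over the 1–24 h spread gives, at 12 h, √[0.357/(0.357 + 0.132)] = 0.85 for CV 30% and √[0.494/(0.494 + 0.132)] = 0.89 for CV 50%. At 24 h the results are 0.96 and 0.97. If everyone had the same dose, or if dose is held constant in the model, this relief disappears and the table applies.

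**What it means with 30 patients.** Power for a correlation r is approximately Φ[atanh(r)·√27 − 1.96]. A true r of 0.50 (assumed; the documents give none) has Φ(2.854 − 1.96) = 81%. Multiplied by 0.92 it becomes 0.46, with power Φ(2.584 − 1.96) = 73%. At the worst corner of the table it becomes 0.19, with power about 16%; at the best it stays at 0.50 and 81%.

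**Day 31.** Counting 28 daily doses from Day 3 would end on Day 30 (3 + 27). But the schedule dispenses ten sublingual units per week; at one unit a day from Day 24 these would last to Day 33 (24 + 9). Windows of plus or minus 2 days allow 3 to 11 days (7 ± 4) between the Day 24 and Day 31 visits. The unit strength is not stated, so neither count settles when the last dose before the Day 31 draw is taken.

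**The case against.** The best defence has four parts.

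First, every pharmacokinetic input is assumed, and the result runs from severe to negligible. With a half-life of 24–36 h and draws 2–14 h after dosing, the multiplier is 0.95–0.99. Dose differences reduce the loss further. This stands: the documents support a direction, not a size.

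Second, a reader might infer that Day 31 levels are taken systematically one to three days after the last dose and so are not comparable with Day 17. The documents do not say so. They name no last dosing day; section 9 treats Day 31 as the end of treatment and lists the post-intervention phase as Days 38 and 45; and the supply of ten units may cover the visit. All that can be said is that time since dose is unstated and may differ between the two visits.

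Third, the momentary level is a reasonable quantity to set beside pupil size or prolactin measured at the same visit. This also stands. The concern applies to suicidality, mood, pain and insomnia, which do not follow the level hour by hour in the way those measures might.

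Fourth, the aim is exploratory, and the case report forms and the dose-adjustment protocol mentioned in section 1.3 are not among the documents, so dose times may be captured there. If so, only the analysis step is missing.

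A reader might also conclude that late draws, say more than 24 h after a dose, should be dropped. That would discard scarce data and selectively remove non-adherent patients, and it is unnecessary once time since dose is in the model.

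**Conclusion.** The point holds as a modest one. As written, the plan relates response to a buprenorphine level whose timing relative to the dose is neither controlled nor recorded, although the ketamine samples in the same schedule are timed in minutes. This adds measurement error that tends to weaken the exploratory level–response relation. The multiplier on the correlation is about 0.37 to 0.99 under the stated assumptions, and the documents cannot narrow that range. They do not support a claim that the loss is large, or that Day 31 samples are necessarily past the end of dosing. No primary or secondary conclusion depends on this analysis.

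**What to change.** At each buprenorphine draw, record the clock time of the draw and the date and time of the last dose. State in section 9 that analyses relating drug level to suicidality, mood, pain and insomnia will include time since dose and current dose as covariates. Leave the same-visit comparisons with pupil and prolactin measures on the momentary level. Exclude no sample because of its timing. If the case report forms already hold these times, say so and add only the covariates.

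The cost is a few form fields at two visits, reliance on dose times reported by patients, and one or two extra covariates in a model with at most 30 patients. No dose, visit or sample changes.

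Current dose belongs in the model for a further reason: dose is adjusted on response and tolerability, so level is also tied to earlier response. Adjusting for current dose does not fully resolve that separate problem, and the write-up should say so.

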by an elevated risk of depression and suicide associated with opioid addiction and withdrawal (1). Although these underscore the negative consequences of opioid abuse, opioids appear to have antidepressant and anti-suicidal properties, as observed in preliminary clinical trials (2). For example, low doses of buprenorphine, a partial mu-opioid receptor (MOR) agonist and kappa opioid receptor (KOR) antagonist, have been reported to be effective as an antidepressant (2) and as an anti-suicidal agent in patients with major depressive disorder (MDD) or borderline personality disorder (3). Similarly, both major depressive and borderline personality disorder patients have altered mu-opioid receptor activity in PET studies (4,5). A recent Israeli study (3) reported that buprenorphine at low doses of 0.1/0.2-0.8 mg per day (mean dose=0.44mg per day) over four weeks reduced suicidal behavior in patients with major depression or borderline personality. The entry criterion was a score of ≥ 11 on the Scale for Suicide Ideation (SSI). The treatment was effective by 2 (but not at 1) weeks, with a mean 4.3-point reduction difference in SSI score, favoring the active drug over placebo. At study completion, the difference was 7.1 points. Antidepressant effects did not attain statistical significance. Withdrawal symptoms were not observed, although formal assessments of dependence/withdrawal were not incorporated into the design.

Another drug recently associated with MOR agonism is ketamine, an anesthetic with rapid-acting antidepressant and anti-suicidal effects (6). A recent meta-analysis indicated that single intravenous doses of ketamine produce significant anti-suicidal effects within 24 hours, lasting at least one week (7), and response rates were about 55%. The mechanisms of action underlying ketamine's antidepressant and anti-suicidal effects have previously been conceptualized broadly as NMDA antagonism (8), yet other candidate NMDA antagonists have not been proven to be effective antidepressants (9). Others have argued that ketamine may induce other glutamatergic effects, such as agonism at the AMPA receptor (10) and modulation of mTOR (11). However, our recent findings about ketamine's relationship with the mu-opioid receptor aligned with previous evidence that ketamine can reduce the need for opioids post-surgery in patients prone to addiction (12). This may, in part, reflect glutamatergic-related plasticity effects.

[figure not shown]

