Analysis of secondary endpoints: The secondary outcome will compare treatment groups on the change in depression symptoms from baseline to day 31 using weekly scores from the MADRS and HDRS. A similar mixed-effects model used for the primary endpoint will be applied. The trajectories of MADRS and HDRS mean scores will be compared between the two groups in the mixed model with statistical significance determined by the p-value for the treatment group by time interaction term. If the groups differ significantly on the MADRS scores, the proportion of responders (i.e., >50% or greater reduction from

baseline to day 31) will be statistically with a 2x2 chi-squared test. The MADRS depression assessment includes one item that assesses suicidal thoughts. Mean scores and standard deviations on this item will be calculated for the K+Buprenorphine and K+Placebo groups, and effect sizes will be calculated using Glass's formula.

Analysis of safety endpoints: Frequencies of side effects, adverse events, and serious adverse events observed during the active treatment phase will be summarized by group, and the most commonly reported adverse events will be tabulated. Changes in suicidality and withdrawal symptoms during the 2-week post intervention phase (days 38 and 45) will be described with means, standard deviations, and ranges for the SSI and MADRS, as well as for clinician and patient ratings of withdrawal (COWS and SOWS). These measures will be compared across groups using independent measures t- tests. No type 1 error correction is planned for safety analyses.

Evaluation of treatment blind: Two-weeks post-intervention (day 45), patients will be asked to endorse one of the following: I think I was taking active medication; I think I was taking placebo; I am unsure if I was taking an active medication or a placebo. Frequency counts and percentages will describe the correct and incorrect guesses.

Missing data: For both primary and secondary endpoints, the mixed-effects models implicitly assume data missing at random. Sensitivity analyses will only be conducted if necessary (e.g., if the missingness is non-ignorable due to high frequency of missingness or if data are not missing at random).

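### The off-drug phase is meant to assess discontinuation symptoms, but no withdrawal scale and no scheduled contact falls between the Day 31 and Day 38 visits, and symptoms recalled at Day 38 enter no planned comparison

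*Combined protocol and SAP*

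**What the plan says.** Section 1.3 (Description of Study Intervention) gives the purpose of the last phase: "After 4 weeks buprenorphine or placebo will be discontinued and patients followed for 2 weeks to assess buprenorphine discontinuation symptoms". Section 6 repeats it: at the end of active treatment "patients will discontinue the study drugs and will be followed up on Days 38 and 45 to monitor for any signs of withdrawal". No taper is described. Section 2.3.1 lists withdrawal among the risks of buprenorphine. Section 2.1 notes that in the earlier low-dose trial no withdrawal was seen, but that "formal assessments of dependence/withdrawal were not incorporated into the design".

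The schedule in section 1.5 marks SOWS (patient-rated) and COWS (clinician-rated) at Days 38 and 45 and nowhere else. Visits from Day 10 to Day 45 each carry a ±2-day window. The only phone contact is Day 5. Study drug is dispensed on Days 3, 10, 17 and 24, with the footnote "Weekly supply of rx provided. Varying dosage depending on response & tolerability".

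Day 38 also has an adverse event review and a concomitant medication review. Section 8.3.4 has the investigator ask at each visit about events since the previous one, and section 8.3.5 adds an open question on how the participant has felt in that time.

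In section 9 (Analysis of safety endpoints) the withdrawal analysis is of "Changes in suicidality and withdrawal symptoms during the 2-week post intervention phase (days 38 and 45"), using means, standard deviations, ranges and between-group t-tests of COWS and SOWS. The by-group summary of adverse events is confined to the active treatment phase.

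**The concern.** The plan names discontinuation symptoms as something to be assessed after stopping. The scales that measure them are first used about a week after the Day 31 visit, with nothing scheduled in between. If the COWS and SOWS scores do not differ between arms, two explanations remain: there was no withdrawal, or there was withdrawal that had gone before the first rating. The planned analysis cannot tell these apart.

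What is at stake is the safety statement, not the efficacy result. A report might say that low-dose buprenorphine was stopped after four weeks without withdrawal, when the first days off drug had not been rated. That would leave part of the limitation that section 2.1 notes in the earlier trial.

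**Working it through.** **Inputs.** From section 1.5: visits at Days 31, 38 and 45, each ±2 days; SOWS and COWS at Days 38 and 45 only; last dispensing on Day 24. From section 6: drug starts after the Day 3 ratings.

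**1. The plan's own durations.** Treatment: 31 − 3 = 28 days = 4 weeks. Off-drug follow-up: 45 − 31 = 14 days = 2 weeks. Both agree with the text.

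**2. Interval from the Day 31 visit to the first withdrawal rating.** Let a and b be the deviations of the Day 31 and Day 38 visits, each from −2 to +2.

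Gap = (38 + b) − (31 + a) = 7 + b − a

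- Nominal: 7 days
- Shortest (a = +2, b = −2): 7 − 4 = 3 days
- Longest (a = −2, b = +2): 7 + 4 = 11 days

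Of the 25 whole-day combinations, 10 give a gap under 7 days. That is a count, not a probability. The second rating falls 14 + b − a days after the Day 31 visit: 14 nominally, 10 to 18 with windows.

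**3. Interval from the last dose.** The last-dose day is not stated for participants who complete treatment, so these rows rest on assumptions. The windows add or subtract 4 days as in step 2.

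| Assumption about the Day 24 supply | Last dose | Days to first rating | With windows |
|---|---|---|---|
| Seven daily doses from Day 24 | 24 + 6 = Day 30 | 8 | 4 to 12 |
| Seven daily doses from Day 25 | 25 + 6 = Day 31 | 7 | 3 to 11 |
| Ten units, one a day from Day 24 | 24 + 9 = Day 33 | 5 | 1 to 9 |
| Ten units, one a day from Day 25 | 25 + 9 = Day 34 | 4 | 0 to 8 |

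The last two rows use the ten sublingual units per week shown in the schedule. Units per day are not stated. These rows would apply only if a participant went on using leftover units after the planned stop. They show why the visit date is not a safe stand-in for the last-dose date.

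**4. Counts from the schedule.** Scheduled contacts between the Day 31 and Day 38 visits: 0. SOWS or COWS ratings at or before Day 31: 0. SSI and MADRS are taken at Day 31, so their change after stopping can be calculated. For COWS and SOWS the only change available is from Day 38 to Day 45.

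**5. Where a symptom that starts after the last dose and is gone by Day 38 would appear.**

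- Withdrawal scale while it is present: none is scheduled.
- Adverse event record: possible, through recall at Day 38 or a call or email from the participant.
- Planned by-group adverse event summary: no, because it covers active treatment only.
- Planned t-tests: these use only the Day 38 and Day 45 scale scores.

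The symptom can be recorded, but it has no place in a planned comparison.

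**The case against.** The strongest reply is that early symptoms are not lost. Day 38 includes an adverse event enquiry covering the time since Day 31. Section 8.3.4 asks for time of onset, severity and time of resolution, and for each episode of an intermittent event. Section 2.3.1 already names withdrawal as a risk, and participants can phone or email. A reader might infer that nothing is recorded in the first week off drug, or that the trial is bound by design to find no withdrawal. The documents support neither: a symptom in that week can become a dated, graded adverse event, and in some window combinations the first rating itself falls inside the first week. What remains is that this capture is recalled and non-specific, and that the planned summary by arm leaves it out.

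A second reply is that the loss cannot be sized. This stands. The documents give no time course for symptoms after stopping these doses. A reader might infer that any reaction of a few days would be missed in everyone; with later onset the same reaction could be present at Day 38. Nor do they say what period SOWS and COWS ask about. If either looks back over the interval, it would pick up some early symptoms, though still from memory.

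Third, withdrawal is not a listed objective or endpoint, and no passage commits the trial to a claim of no withdrawal. It is also an inference, not a statement in the plan, that this phase is there to make good the earlier trial's omission. Both are correct and limit the weight of the point. But sections 1.3 and 6 do state the purpose, and section 9 tests the scores.

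Fourth, remote symptom reports from participants with suicidal ideation would need someone to look at them. That is fair and belongs in the cost.

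**Conclusion.** The point holds in limited form. Between the Day 31 and Day 38 visits there is no withdrawal scale and no scheduled contact: 7 days nominally, 3 to 11 days visit to visit with the windows. Measured from the last dose, the interval is unknown for completers because that date is not specified. Symptoms that begin and settle in that time depend on recall at Day 38 or on the participant making contact, and would enter no planned comparison between arms. There is also no on-drug COWS or SOWS value against which to judge the off-drug scores.

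The day arithmetic needs no assumption beyond the schedule. The reading that the Day 38 scores do not cover earlier days assumes that the scales describe the participant at about the time of the visit, which the documents do not say. They do not show that withdrawal will occur, or what share would be missed, and no such figure should be attached to this point. The primary endpoint at Day 31 is unaffected. This is a worthwhile, inexpensive improvement to a stated safety purpose.

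**What to change.** 1. Add SOWS and COWS at the Day 31 visit as an on-drug reference.
2. Collect the self-report SOWS remotely through REDCap, which the trial already uses, on two or three fixed days between Days 31 and 38, the same days in both arms.
3. At Day 38, add one item on the worst symptoms since the last dose, and record the last-dose date for every participant.
4. In section 9, add a by-arm comparison of the maximum SOWS from stopping to Day 38, taking the Day 31 value into account, beside the planned Day 38 and Day 45 comparisons. Report how many remote entries were completed in each arm, since a maximum depends on the number of readings.
5. Extend the by-group adverse event summary through Day 45.
6. State the period that each withdrawal scale asks about.

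If the extra ratings are not adopted, limit any statement that withdrawal was absent to the days actually rated.

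Cost: two scales at an existing visit, two or three short online questionnaires, one item, one date field and a few analysis lines. For participants it is a few minutes. Existing staff would need to make a light check of the remote entries. These steps change measurement and reporting only, not dose or care.
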